6.1.6. Pooling of Sites

Analyses will be based on data pooled across investigative sites.

6.1.7. Data Adjustments/Handling/Conventions

All collected data will be presented in listings. Data not subject to analysis according to this plan will not appear in any tables or graphs but will be included only in the data listings.

All *P* values will be displayed to four decimal places and rounded using standard scientific notation (e.g., 0.XXXX). If a *P* value less than 0.0001 occurs it will be shown in tables as < 0.0001.

Adverse events in the clinical database will be coded using the MedDRA version 24.0.

A treatment related AE is any AE with a relationship to the study drug of possibly related, probably related, definitely related or missing relationship to the study drug.

If partial dates occur, the convention for replacing missing dates for the purpose of statistical analysis is as follows: if just day is missing then the day assigned is the first day of the month or the date of first dose (if in the same month), whichever is later; if just month is missing then the month assigned is the month of the first dose, unless that results in a date before the first dose in which case the month after the first dose is used; and if both month and day are missing then the

month assigned is the month of the first dose and the day assigned is either the first day of the month or the first dose date, whichever is later.

If partial times occur, the convention is as follows: if the missing time occurs on the day of the first dose and both the hour and minute are missing then the time assigned is the time of the first dose, otherwise if both the hour and minute are missing and the date is not the date of first dose the time assigned is 12:00; if the date is the same as the date of the first dose and only hour is missing the hour assigned is 12 or the hour of first dose, whichever is later, and if the date is the same as the date of first dose and only the minute is missing the minute assigned is 30 or the minute of first dose, whichever is later. Otherwise the hour assigned is 12 if the hour is missing and the date is not the same as the date of first dose and the minute assigned is 30 is the the date is not the same as the date of first dose.

7. Study Participants and Demographics

Summaries for disposition of participants and demographic and baseline characteristics will be presented by treatment group (treatment cohort and overall in Part 2).

7.1. Disposition of Participants and Withdrawals

Disposition of participants in Part 1 will include, but not limited to, the following:

- The number of participants who
 - o Screened
 - Failed screening
 - Reasons failed screening
 - Placebo Run-in/Placebo Run-in Safety Set
 - Not completed
 - Reasons not completed
 - o Lixivaptan Titration/Lixivaptan Titration Safety Set
 - Not completed
 - Reasons not completed
- The number and percentage (percentage is calculated based on all the randomized participants) of participants who
 - Randomized/ITT
 - Treated/mITT/Randomized Safety Set
 - Completers/PEAS
 - On-treatment completers

- Off-treatment completers
- At least one on-treatment eGFR assessment/SEAS
- Discontinued from study drug early and reasons
- Not completed in Part 1 and reasons
- In PPAS

Disposition of participants in Part 2 will include, but not limited to, the following:

- The number and percentage (percentage is calculated based on all the continuing participants in Part 2) of participants who
 - Continued in Part 2
 - Treated/P2SS
 - At least 1 off-treatment eGFR/P2EAS
 - Discontinued from study drug early and reasons
 - Not completed in Part 2 and reasons

Note that Lixivaptan Treated Safety Set for Parts 1 and 2 combined consists of the participants who are randomized and treated (Randomized Safety Set) in lixivaptan treatment group in Part 1 and the participants who are treated (P2SS) in Part 1/Part 2 - Placebo/Lixivaptan cohort in Part 2.

7.2. **Protocol Deviations**

Protocol deviations will be tracked, recorded, and reviewed prior to database lock, following the Protocol Deviation Guidance Plan for this study.

Protocol deviations will be classified as "Important" or "Not Important".

Important protocol deviations include:

- Enrollment of a participant that did not meet inclusion criteria of the study/Enrollment of a participant that met exclusion criteria of the study.
- Missed safety assessments during Screening that are required for the thorough vetting of study inclusion/exclusion criteria are considered important deviations. They will be documented through failure of the respective Inclusion or Exclusion Criterion.
- Informed Consent Form (ICF) not obtained, or obtained after initiation of respective study procedures, important deviation from GCP consenting procedure, such as wrong version used, missing signature(s) and/ or date(s), ICF signed prior to IRB/IEC approval, other important deviation from GCP consenting process
- Prohibited Medications Use of a prohibited concomitant medication
- Dosing Adherence defined as taking less than 80% of the protocol-specified amount of study drug across the study

- Randomization error
- Mis-stratification of a participant within IRT system
- Drug dispensation without IRT assignment, incorrect drug kit administration, dose mistakes over inappropriate titration/re-titration
- Used the study drug with incorrect storage (temperature excursions, improper transport, security, etc.) which compromises Investigational Product safety or chemical activity
- MRI examination of kidneys during the screening, in Follow Up Period I, in Follow Up Period II not done/done with deviation from imaging technique described in Imaging manual
- Serum creatinine blood sample from Screening, Placebo Run-In, Follow-up Period I (or for participants who discontinue treatment prior to Visit 22, from the Follow-up Period following study drug treatment discontinuation) and Follow-up Period II not collected/ not sent to Central Lab for evaluation/ non evaluable, laboratory manual requirements not followed, serum creatinine result missing for any other reason, age/ sex/ race data missing or incomplete
- Liver Chemistry laboratory sample not collected/ not performed as required per protocol
- Repeat Liver Chemistry tests not performed within 48 hours of knowledge that aminotransferase levels >3 x ULN or total bilirubin >2 x ULN

The following deviation codes will be used to categorize/summarize the important protocol deviation above:

- Inclusion Criteria
- Exclusion Criteria
- Study Drug
- Assessment Safety
- Assessment Efficacy
- Lab Endpoint Data
- Visit Window
- Informed Consent
- Prohibited Medication
- Other

Study participants will be excluded from the PPAS if they meet any of the following criteria:

- Participant who did not meet all inclusion and exclusion criteria
- Placebo randomized participant who received lixivaptan treatment

- Lixivaptan randomized subject who received placebo treatment only throughout study
- Any participant who received protocol prohibited medications that could affect efficacy
- Participant with overall study treatment compliance of less than 80%

The protocol deviations that impact the analysis populations will be recorded once identified and periodically reviewed by the study team. The final decision regarding inclusion and exclusion of participants from the analysis populations will be determined during a (blinded) data review meeting before any unblinding occurs or database freeze/lock, with input from the Clinical, Biostatistics, Data Management and Clinical Operations team members and approval from the Sponsor.

Additionally, inclusion and exclusion criteria not met and reasons for screen failures will be listed.

7.3. Demographics and Other Baseline Characteristics

Summary statistics for age, sex, race, ethnicity, height, weight, and BMI will be presented by treatment group.

For the continuous variables, the number of non-missing values and the mean, standard deviation, median, minimum, and maximum will be tabulated.

For the categorical variables, the counts and proportions of each value will be tabulated.

These analyses will be conducted for the Randomized Safety Set and PEAS (Part 1) and P2SS and P2EAS (Part 2).

The number and percent of participants with a family history of ADPKD, the counts and percentages of each method used to diagnose ADPKD, the counts and percentages of each Mayo Clinic ADPKD Classification, the counts and percentages of each CKD stage, and the time since diagnosis will be presented by treatment group for Part 1. The number and percent of participants prior treated with tolvaptan and associated safety information will be summarized by treatment group for Part 1. The number and percent of participants reporting various medical histories, grouped by MedDRA system organ class and preferred term (coded using MedDRA v.24), will be tabulated by treatment group. This analysis will be conducted for the Randomized Safety Set and PEAS (Part 1) and P2SS and P2EAS (Part 2).

In addition, the above summary will be presented for all the participants who entered in the Lixivaptan Titration Period (Lixivaptan Treated Safety Set).

7.4. Exposure and Compliance

Exposure and compliance will be presented for Randomized Safety Set during the Double-Blind, Randomized Treatment Period (Part 1) and P2SS during the Maintenance Treatment Period (Part 2).

The duration of exposure will be presented in days and calculated as the date of last dose in treatment period minus the date of first dose in treatment period, plus one. Duration of exposure

and total dose taken (mg) will be summarized using descriptive statistics by treatment group (treatment cohort in Part 2).

Compliance to study drug is calculated by dividing the total capsules taken by the total capsules the participants were scheduled to take during the treatment period:

Treatment Compliance (%) = $\frac{total Capsules Taken}{Total Capsules Scheduled} \ge 100$

Dosing compliance will be summarized using descriptive statistics by treatment group (treatment cohort in Part 2). The number and percentages of participants who are < 80% compliant and $\ge 80\%$ compliant overall in the study will be summarized.

8. Efficacy Analysis

8.1. Definition of Completer and Non-completer

Part 1 completer and non-completer will be defined as the following:

- On-treatment completer: all the randomized participants who take double-blind study drug in accordance with the protocol through Visit 22 (Week 52), and complete some or all of their required trial visits/assessments through Visit 22 and have at least one follow-up serum creatinine assessment during off-treatment Follow-up Period I.
- Off-treatment completer: all the randomized participants who permanently discontinue double-blind study drug (or never begin double-blind treatment) and complete some or all of their required study visits/assessments through Visit 22 and have at least one follow-up serum creatinine assessment during Follow-up Period I.
- Non-completer: all the randomized participants who take the study drug (or never take the study drug) but do not complete the Visit 22/ET visit or complete Visit 22/ET visit and do not have at least 1 follow up serum creatinine assessment during Follow-up Period I.

Part 2 completer and non-completer will be defined as the following:

- On-treatment completer: all the randomized participants who enter Part 2 of the study, take open-label study drug in accordance with the protocol through Visit 42 (Week 104), and complete some or all of their required study visits/assessments through Visit 42 and have at least one follow-up serum creatinine assessment during Follow-up Period II.
- Off-treatment completer: all the randomized participants who enter Part 2 of the study, but permanently discontinue open-label study drug (or never begin open-label treatment) and complete some or all of their required study visits/assessments through Visit 42 and have at least one follow-up serum creatinine assessment during Follow-up Period II.
- Non-completer: all the randomized participants who enter Part 2 of the study, take the study drug (or never take the study drug) but do not complete the Visit 42/ET visit or

complete Visit 42/ET visit but do not have at least 1 follow up serum creatinine assessment during Follow-up Period II.

8.2. Primary Efficacy Analysis (Part 1)

The primary efficacy endpoint is the annualized change in eGFR (2021 CKD-EPIcr_R), with restriction as defined below, for serum creatinine from baseline (mean of 3 eGFR determinations obtained during Screening and Placebo Run-in Periods, i.e., Visits 1a (or 1b, if required), Visit 2, and Visit 3) to final assessment (mean of 3 eGFR determinations obtained during Follow-up Period I after Week 52 for on-treatment completers or, for participants who discontinue study drug treatment prior to Week 52 [Visit 22], 8 to 28 days following study drug treatment discontinuation).

Restriction refers to all annualized changes in eGFR of participants that discontinued study drug treatment that are greater (or less) than the maximum (or minimum) of the annualized eGFR change based on off-treatment serum creatinine assessments of all on-treatment completers regardless of treatment groups. For such participants, the annualized change in eGFR will assume the maximum (or minimum) value of all on-treatment completers to reduce the impact of the outliers created by the annualized eGFR change in participants that early discontinued study drug treatment.

The primary estimand for the primary efficacy endpoint is the between-treatment group difference in the change from baseline in off-treatment eGFR if all the participants in the PEAS had tolerated and adhered to their treatment for 52 weeks. Potential bias due to randomized participants prematurely discontinuing from double-blind treatment will be handled by annualizing the changes from baseline by multiplying each participant's change from baseline by 365.25 days divided by the duration from the median of the collection dates of the baseline eGFR assessments to the median of the collection dates of the 3 eGFR assessments made during the post-treatment, follow-up period immediately (8-28 days) following study drug discontinuation.

An analysis of covariance (ANCOVA) model with fixed effects for treatment group (0=placebo, 1=lixivaptan) and the randomization stratification factors (CKD stage [CKD2 versus CKD3/4] and Mayo Clinic ADPKD Image Classification [1C, 1D, or 1E]) and the baseline eGFR as a covariate.

The following SAS code will be used for the primary efficacy analysis:

```
PROC GLM ALPHA =0.01;
```

```
CLASS TREATMENT CKD_STAGE MAYO_CLASS;
MODEL ANNUALIZED_CHANGE = TREATMENT BASELINE CKD_STAGE MAYO_CLASS/SOLUTION
SS3 CLPARM;
LSMEANS TREATMENT/STDERR
ESTIMATE "Treatment Effect: Lixivaptan - Placebo" TREATMENT -1 1;
```

RUN;

This analysis assumes that data are missing at random. The stratification by CKD stage at the time of randomization will be based on the baseline eGFR creatinine equation in effect at the

time of baseline visits. However, all efficacy analyses of change in eGFR will be based on the CKD-EPIcr_R equation.

The primary efficacy analysis will be performed on the PEAS at the 1% level of significance (p<0.01).

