3.7. Sample Size

Part 1:

Based on the results of the REPRISE trial with tolvaptan (Torres et al, 2017), it is assumed that the standard deviation for the primary efficacy endpoint, change from baseline to post-treatment follow-up in mean eGFR, is 6.20 mL per minute per 1.73 m². Assuming a between-treatment group difference of -1.40 mL per minute per 1.73 m² and a randomization ratio of 2:1 for lixivaptan to placebo, a sample size estimate of 1314 participants (438 placebo-treated participants and 876 lixivaptan-treated participants) is required to achieve 90% power at a significance level of 0.01. This estimate has been adjusted up to 1350 participants (450 placebo participants and 900 lixivaptan participants). It is estimated that approximately 2250 participants will need to be screened in order to randomize 1350 participants.

Part 2:

This is a convenience sample based on the number of participants who elect to continue into Part 2. It is estimated that approximately 1350 participants will be randomized in Part 1. All participants except those who discontinue due to an adverse event or withdraw consent will continue into Part 2. Approximately 90% (1215) of Part 1 participants are anticipated to continue into Part 2.

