8.2.1.2. Secondary Sensitivity Analyses

Sensitivity on the annualized change in eGFR (2021 CKD-EPIcr_R) with restriction from baseline to final assessment (mean of 3 eGFR values obtained during Follow-up Period I after Week 52 for on-treatment completers or, for participants who discontinue study drug treatment prior to Visit 22, during the Follow-up Period 8 to 28 days following study drug treatment discontinuation) using a weighted ANCOVA will be performed on the PEAS. The weighted analysis is based on the reciprocal of the estimated variance of the "estimated slopes" for participants based on individual off-treatment eGFR values obtained during Follow-up Period I after Week 52 for on-treatment completers or, for participants who discontinue study drug treatment prior to Visit 22, during the Follow-up Period 8 to 28 days following study drug treatment for participants based on individual off-treatment eGFR values obtained during Follow-up Period I after Week 52 for on-treatment completers or, for participants who discontinue study drug treatment prior to Visit 22, during the Follow-up Period 8 to 28 days following study drug treatment prior to Visit 22, during the Follow-up Period 8 to 28 days following study drug treatment discontinuation). The detailed algorithm to derive the weight is provided in an Appendix.

The weighted ANCOVA model will include fixed effects for treatment group and the randomization stratification factors (CKD stage [CKD2 versus CKD3/4] and Mayo Clinic ADPKD Image Classification [1C, 1D, or 1E]) and the baseline eGFR as a covariate.

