8.3.1. Annualized Rate of Change (Slope) in eGFR

The first secondary efficacy endpoint is annualized rate of change (slope) in eGFR (2021 CKD-EPIcr_R) at on-treatment timepoints using the SEAS. This annualized rate of change (slope) in eGFR on treatment will be estimated by utilizing a mixed-effects model for repeated measures (MMRM) on the observed changes in eGFR from baseline (mean of the 3 eGFR values obtained during the Screening and Placebo Run-in Periods) to all visits with on-treatment eGFR values during the Double-Blind, Randomized Treatment Period visits, i.e., Visit 10 (Week 4) to Visit 22 (Week 52), while on study drug treatment. Any eGFR values obtained 1 day after study drug treatment during the Double-Blind, Randomized Treatment Period are excluded from the analysis. The MMRM will include treatment group, visit, treatment group-by-visit, and randomization stratification factors (CKD stage [CKD2 versus CKD3/4] and Mayo Clinic ADPKD Image Classification [1C, 1D, or 1E]) as fixed effects, baseline eGFR as a covariate, and the baseline-by-visit interaction. An unstructured variance-covariance matrix is assumed for the repeated measures.

Analysis of MMRM will be applied to the change from baseline in eGFR among the 13 ontreatment visits: visit 10 (week 4), visit 11 (week 8),visit 12 (week 12), visit 13 (week 16), visit 14 (week 20), visit 15 (week 24), visit 16 (week 28), visit 17 (week 32), visit 18 (week 36), visit 19 (week 40), visit 20 (week 44), visit 21 (week 48) and visit 22 (week 52). The median of the 13 visits is the 7th visit, i.e., Visit 16 (Week 28).

To estimate the slope in eGFR on treatment, the contrast coefficients of the linear trend for visits will become -6, -5, -4, -3, -2, -1, 0, 1, 2, 3, 4, 5, 6. Under assumptions that the annualized slope and acute hemodynamic effect are constant over time, this contrast can be used to estimate the slope (note that the acute hemodynamic effect is eliminated by the contrast). The resulted estimate corresponding to those coefficients will be slope (per week) multiplied by 728 (-6*4 - 5*8 -4*12 -3*16 -2*20 -1*24 +0*28 +1*32 +2*36 +3*40 +4*44 +5*48 +6*52=728) or annualized slope multiplied by 14 (728/52=14).

Thus, the coefficients of the linear trend contrast of these 13 visits to estimate the annualized slope are -6/14, -5/14, -4/14, -3/14, -2/14, -1/14, 0/14, 1/14, 2/14, 3/14, 4/14, 5/14, 6/14.

Example SAS code is shown below:

```
PROC MIXED EMPIRICAL;
```

RUN;

```

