A significance level of 0.01 (two-sided) will be used to declare statistical significance of treatment effect at the final analysis. Antilog (with a base of 10) of the treatment effect and 99% confidence intervals (99% CIs) derived from the model (in a log10 scale) provide a ratio of geometric means of the relative change (ratio) from baseline in htTKV (i.e., 100% plus annualized percent change).

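### With 2:1 allocation and unequal discontinuation, the pooled-variance primary ANCOVA departs modestly from its 1% level; a robust standard error would remove this

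*SAP*

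**What the plan says.** SAP 8.2 defines the primary endpoint as the change in eGFR from baseline to the off-treatment follow-up, scaled to one year by the participant's own elapsed time. For those who stop early, the follow-up is the one 8 to 28 days after stopping. Their annualised values are capped at the smallest and largest values seen among on-treatment completers.

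The test is an unweighted ANCOVA, coded as "PROC GLM ALPHA =0.01", with treatment, the two stratification factors and baseline eGFR. There is no weight and no robust variance. On level, the SAP says: "The primary efficacy analysis will be performed on the PEAS at the 1% level of significance".

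The SAP shows in two places that it knows annualising makes early stoppers extreme. One is the cap. The other is a weighted ANCOVA in 8.2.1.2, described as follows: "The weighted analysis is based on the reciprocal of the estimated variance of the" participants' estimated slopes. That analysis is a secondary sensitivity analysis.

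For the on-treatment slope endpoint in 8.3.1 the SAP uses "PROC MIXED EMPIRICAL", a sandwich variance. The same option appears in 8.2.1.3, 8.3.1.1 and 8.5, but not in the primary analysis.

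**The concern.** Dividing by a short duration D multiplies the noise in a change by 1/D, and its variance by 1/D². If one arm has more early stoppers, that arm has the larger outcome variance. A pooled standard error weights the two arm variances by sample size, whereas the true variance of the difference weights them by the reciprocal of sample size. With equal arms the two agree. With 900 and 450 they do not, so the p-value is no longer exactly at its stated level.

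The primary test is run at a strict 1% and is the gate to both secondary endpoints (SAP 6.1.3). Its level should not depend on which arm happens to stop more often.

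**Working it through.** **1. Reproduce the plan's own figure.** SAP 3.7 gives the SD: "change from baseline to post-treatment follow-up in mean eGFR, is 6.20 mL per minute". It gives the effect: "Assuming a between-treatment group difference of -1.40 mL per minute". Allocation is 2:1, and the resulting sample "is required to achieve 90% power at a significance level of 0.01". With a two-sided test:

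n(placebo) = (1 + 1/2) × (6.20/1.40)² × (2.576 + 1.282)² ≈ 1.5 × 19.61 × 14.88 ≈ 437.7, so 438, and 3 × 438 = 1314 in total.

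This matches. A one-sided test would give 383 and 1149, so the design is two-sided. SAP 8.3.2 says so outright only for htTKV: "A significance level of 0.01 (two-sided) will be used to declare statistical significance". At 450/900 the nominal power is 90.9%.

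**2. How far duration changes the variance.** Elapsed time runs from the median baseline date to the median follow-up date. It is taken as about 9 weeks plus weeks on randomised treatment: run-in, 5 to 6 weeks of titration, and the gap to follow-up.

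- Completer: 61 weeks = 1.169 years.
- Stops at week 4: 13 weeks = 0.249 years; (1.169/0.249)² ≈ 22.
- Stops at week 12: 21 weeks = 0.402 years; (1.169/0.402)² ≈ 8.5.

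The part of the variance that does not scale with time is therefore inflated about 22-fold or 8.5-fold, before the cap.

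**3. Size of the pooled test.** Let r be the lixivaptan variance divided by the placebo variance v.

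- True variance of the difference: v/450 + rv/900 = v(2 + r)/900.
- Pooled variance: [(450v + 900rv)/1350] × (1/450 + 1/900) = v(1 + 2r)/900.
- Actual size: 2 × {1 − Φ(2.576 × √[(1 + 2r)/(2 + r)])}.

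| r | size at 900/450 | size at 675/675 |
|---|---|---|
| 0.67 | 1.59% | 1.00% |
| 0.8 | 1.31% | 1.00% |
| 1 | 1.00% | 1.00% |
| 1.25 | 0.75% | 1.00% |
| 1.5 | 0.59% | 1.00% |

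**4. Plausible values of r with the cap.** Arm variances were simulated for 900/450, with 8000 two-group runs per scenario. The assumptions, none of them from the documents, were:

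- a completer's annualised SD is 6.20;
- 30%, 60% or 100% of that variance does not scale with time;
- stopping is either uniform over the year or mostly early.

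| Discontinuation, lixivaptan/placebo | size of the nominal 1% test |
|---|---|
| 10% / 10% | 1.00% |
| 12% / 6% | 0.78–0.93% |
| 15% / 5% | 0.67–0.88% |
| 5% / 15% | 1.13–1.44% |

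Worked example at 15%/5%, uniform stopping, 100% share: the SDs are 7.21 and 6.55, so r = 7.21²/6.55² = 1.21. Then √(3.42/3.21) = 1.032, the effective critical value is 2.66, and the size is 0.78%.

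Over all scenarios an unequal-variance standard error gave simulated sizes of 0.9–1.3%, scattered around 1% (Monte Carlo SE about 0.1 point).

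**5. The planned model itself.** The full ANCOVA was also simulated with the cap.

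- Pooled size: about 0.86–0.99% at 15%/5% and 1.10–1.13% at 5%/15%, with about 1.0% at equal rates.
- HC3 size: 0.94–1.13%.
- HC3 gained about 0.5–2.3 points of power at 15%/5%.

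Steps 4 and 5 together give the rounded ranges of 0.7–1.0% and 1.1–1.4%.

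**The case against.** The strongest reply is that the effect is small and usually in the safe direction. If an aquaretic drug causes more stopping, the larger arm has the larger variance and the test is conservative. Inflation needs more stopping on placebo, and nothing in the documents predicts that. Only people who titrated to at least 100 mg BID are randomised, which limits differential intolerance. The protocol synopsis gives only about 90% completion overall. A 12%/6% split matches that figure ((900 × 12% + 450 × 6%)/1350 = 10%) and leaves the size at 0.78–0.93%. The PEAS also omits discontinuers with no off-treatment eGFR, so fewer short-duration records enter. All of this stands, and it is why the point is modest.

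It can also be said that the SAP already probes the issue through the cap, the weighted ANCOVA, a completers-only analysis and imputed analyses. These would expose fragility, but none of them changes the primary standard error. The weighted analysis is not a ready substitute either. It changes the estimate, and the Appendix divides the variance of the change by duration, where dividing a change by D calls for D².

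A reader might infer that the primary test has an inflated false-positive rate. The documents do not support that: the direction depends on which arm stops more, and no arm-specific rate is given. Nor should calculations without the cap be used to describe this test. They give 1.20–1.99% at 5%/15%, but the uncapped endpoint is only a sensitivity analysis (SAP 8.2.1.1).

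**Conclusion.** The point holds as a modest one. The primary standard error rests on an equal-variance assumption that the endpoint breaks by construction, and 2:1 allocation lets the breach reach the p-value when discontinuation differs by arm. With the cap and assumed rates of 15% versus 5%, the size is about 0.7–1.0% if lixivaptan stops more, with about 0.5–2 points of power lost, and about 1.1–1.4% if placebo stops more. With equal discontinuation the test is valid.

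These figures rest on assumed arm-specific rates, stopping times, elapsed times and variance shares. The absolute power depends further on whether 6.20 is read as the SD of the raw or of the annualised change, so only the difference in power is given. SAP Section 12 records that five participants were randomised and that no statistical analyses will be run. The point therefore concerns the plan and any reuse of it, not a result.

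**What to change.** In SAP 8.2, keep the endpoint, the cap, the ANCOVA terms and the point estimate. Pre-specify that the primary standard error, p-value and 99% CI come from a heteroscedasticity-consistent estimator. This can be HC3, or PROC MIXED with the EMPIRICAL option and the participant as subject, as the SAP already does in 8.2.1.3, 8.3.1, 8.3.1.1 and 8.5. The pooled PROC GLM result can be kept as a supportive analysis.

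The work is a change of procedure or option in one program. The small-sample cost is negligible at 1350 participants. If placebo discontinues more, nominal power falls by about 0.7–2.7 points under the same assumptions, because the excess size is removed.
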